### 8.2.5 Performance Status

Performance status is to be assessed using the Eastern Cooperative Oncology Group (ECOG) performance status scale for all patients at the time points designated in the SoA (Table 2). The ECOG performance status scale, with corresponding Karnofsky performance status score equivalents, is presented in Table 9.

**Table 9: Eastern Cooperative Oncology Group Performance Status Scale, with Equivalent Karnofsky Performance Status Scores**

ECOG a		Karnofsky b	
Score	Criterion	%	Criterion
0	Normal activity	100	Normal; no complaints; no evidence of disease
		90	Able to carry on normal activity; minor signs or symptoms of disease
1	Symptoms but ambulatory	80	Normal activity with effort; some signs or symptoms of disease
		70	Cares for self; unable to carry on normal activity or do active work
2	In bed <50% of time	60	Requires occasional assistance but is able to care for most of his/her needs
		50	Requires considerable assistance and frequent medical care
3	In bed >50% of time	40	Disabled, requires special care and assistance
		30	Severely disabled; hospitalization is indicated though death is not imminent
4	100% bedridden	20	Very sick; hospitalization is necessary
		10	Moribund; fatal processes progressing rapidly
5	Dead	0	Dead

a Oken MM, Creech RH, Tormey DC, Horton J, Davis TE, McFadden ET, Carbone PP. Toxicity and response criteria of the Eastern Cooperative Oncology Group. Am J Clin Oncol. 1982;5:649-655.

b Mor V, Laliberte L, Morris JN, Wiemann M. The Karnofsky Performance Status Scale: an examination of its reliability and validity in a research setting. Cancer. 1984;53:2002-2007.

### 8.2.6 Electrocardiograms

At Screening, 12-lead electrocardiograms (ECGs) are to be performed in triplicate, with each measurement separated by 2 minutes. The average of the 3 Screening ECGs will be used to calculate QTc to determine study eligibility. The Investigator (or designee) will perform a clinical assessment of each 12 lead ECG.

ECGs are to be performed at the designated time points in the SoA (Table 2). ECG measurements should be taken after the patient has been resting in the supine or reclined position.

Additional 12 lead ECGs may be performed at other times if judged to be clinically appropriate or if the ongoing review of the data suggests a more detailed assessment of ECGs is required.

### 8.2.7 Clinical Safety Laboratory Assessments

See [Section 10.5](#) for the list of clinical laboratory tests to be performed and the SoA ([Table 2](#)) for the timing and frequency. Additional clinical laboratory evaluations will be performed at other times if judged to be clinically appropriate or if the ongoing review of the data suggests a more detailed assessment of clinical laboratory safety evaluations is required (e.g., repeat testing as required to confirm results).

The Investigator must review the laboratory reports, document this review, and record any clinically relevant changes occurring during the study in the AE section of the eCRF. The laboratory reports must be filed with the source documents. Clinically significant abnormal laboratory findings are those which are not associated with the underlying disease, unless judged by the Investigator to be more severe than expected for the patient's condition.

If such values do not return to normal/baseline within a period of time judged reasonable by the Investigator, the etiology should be identified, and the Sponsor notified.

All protocol-required laboratory assessments, as defined in [Section 10.5](#), must be conducted in accordance with the laboratory manual and the SoA.

## 8.3 Safety Parameters and Definitions

Adverse events observed or discovered by the Investigator in this study, as well as information on AEs reported by the patient, whether or not there is a suspicious causal association with the study medication, are required to be reported in accordance with the following requirement.

### 8.3.1 Definition of Adverse Events

An AE is any untoward medical occurrence in a patient or clinical investigation subject administered a pharmaceutical product and which does not necessarily have to have a causal relationship with this treatment.

An AE can therefore be any of the following:

- Any abnormal laboratory test results (hematology, clinical chemistry, or urinalysis) or other safety assessments (e.g., ECG, radiological scans, vital signs measurements), including those that worsen from baseline, considered clinically significant in the medical and scientific judgment of the Investigator (i.e., but not related to progression of underlying disease).
- Worsening of signs and symptoms of the malignancy under study drug treatment.
- Exacerbation of a chronic or intermittent pre-existing condition including either an increase in frequency and/or intensity of the condition.
- New conditions detected or diagnosed after study drug administration even though it may have been present before the start of the study.

- Related to a protocol-mandated intervention, including those that occur prior to assignment of study treatment (e.g., screening invasive procedures such as biopsies).
- Signs, symptoms, or the clinical sequelae of a suspected overdose of either study drug or a concomitant medication. Overdose per se will not be reported as an AE/SAE unless it is an intentional overdose taken with possible suicidal/self-harming intent. Such overdoses should be reported regardless of sequelae.

Events NOT meeting the AEs definition:

- Any clinically significant abnormal laboratory findings or other abnormal safety assessments associated with the underlying disease, unless judged by the Investigator to be more severe than expected for the participant's condition.
- The disease/disorder being studied or its progression, signs, or symptoms, unless more severe than expected for the participant's condition.
- Medical or surgical procedure (e.g., endoscopy, appendectomy). The condition that leads to the procedure is the AE.
- Situations in which an untoward medical occurrence did not occur (social and/or convenience admission to a hospital).
- Anticipated day-to-day fluctuations of pre-existing disease(s) or condition(s) present or detected at the start of the study that do not worsen overall.

### 8.3.2 Definition of Serious Adverse Event

An SAE is defined as any untoward medical occurrence that at any dose meets any of the following criteria:

- Results in death
- Is life-threatening

The term 'life-threatening' in the definition of 'serious' refers to an event in which the patient was at risk of death at the time of the event. It does not refer to an event which hypothetically might have caused death, if it were more severe.

- Requires inpatient hospitalization or prolongation of existing hospitalization

In general, hospitalization signifies that the patient has been detained (usually involving at least an overnight stay) at the hospital or emergency ward for observation and/or treatment that would not have been appropriate in the physician's office or outpatient setting.

Complications that occur during hospitalization are AEs. If a complication prolongs hospitalization or fulfills any other serious criteria, the event is serious. When in doubt as to whether "hospitalization" occurred or was necessary, the AE should be considered serious.

- Results in persistent or significant disability/incapacity

The term disability means a substantial disruption of a patient's ability to conduct normal life functions.

- Is a congenital anomaly/birth defect
- Is a significant medical event in the Investigator's judgement

Medical or scientific judgment should be exercised in deciding whether SAE reporting is appropriate in other situations such as important medical events that may not be immediately life-threatening or result in death or hospitalization but may jeopardize the participant or may require medical or surgical intervention to prevent one of the other outcomes listed in the above definition. These events should usually be considered serious.

Examples of such events are intensive treatment in an emergency room or at home for allergic bronchospasm, blood dyscrasias, or convulsions that do not result in hospitalization, or development of drug dependency or drug abuse.

The terms "severe" and "serious" are not synonymous. Severity refers to the intensity of an AE (e.g., rated as mild, moderate, or severe, or according to the NCI CTCAE, version 5.0).

Severity and seriousness need to be independently assessed for each AE recorded on the eCRF.

#### 8.3.2.1 Hospitalization

Some events that require inpatient hospital care or prolongation of existing hospitalization may not be considered as SAE. When hospitalization is not associated with an AE as supported by evidence, the hospitalization will not be considered as SAE, the following "hospitalizations" should not per se constitute a SAE:

- Inpatient hospital care or prolongation of existing hospitalization is a result of other factors rather than an SAE (e.g., pre-existing conditions)
- Inpatient hospital care appointed or scheduled prior to the study (e.g., hospitalization for routine physical examination, patient education and planned medical operations, social causes etc.).

The causes of the above hospitalization events must be clearly documented in the medical records.

#### 8.3.2.2 Disease Progression

Progression of the malignancy under study (including signs and symptoms of progression) should not be recorded as an AE or SAE. If the Investigator believes that the progression of malignancy under study is related to the study drug or the progression of the malignancy led to death, the progression should be reported as an SAE.

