**Table 10: Adverse Event Severity Grading**

Grade	Non-CTCAE Severity	Definition
1	Mild	Asymptomatic or mild symptoms; clinical or diagnostic observations only; or intervention not indicated
2	Moderate	Minimal, local, or non-invasive intervention indicated; or limiting age-appropriate instrumental ADL b
3	Severe	Medically significant, but not immediately life-threatening; hospitalization or prolongation of hospitalization indicated; disabling; or limiting self-care ADL c
4	Life-Threatening	Urgent intervention indicated
5	Fatal	Results in patient's death

NCI CTCAE = National Cancer Institute Common Terminology Criteria for Adverse Events.

ADL= Activities of Daily Living

b Instrumental ADL refers to preparing meals, shopping for groceries or clothes, using the telephone, managing money, etc.

c Self -care ADL refer to bathing, dressing, and undressing, feeding self, using the toilet, taking medications, and not bedridden

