9.1 ADVERSE EVENTS

Adverse events (AEs) will be coded to the system organ class (SOC) and preferred term (PT) using MedDRA version 25.1. Toxicity grading is based on the National Cancer Institute Common Terminology Criteria for Adverse Events (NCI CTCAE) version 5.0.

All AE summaries will be limited to the treatment-emergent adverse events (TEAEs). A TEAE is defined as an AE that has an onset or a worsening in severity during or after the first dose of study drug and up to 30 days after the last dose of study drug, or one day prior to the subsequent anti-tumor therapy, whichever occurs earlier. An AE that has a change in severity will be recorded as two separate AEs on the CRF under the same SOC/PT of different severity levels. If an AE has a missing onset date, it will be considered as a TEAE in the below situations:

- An AE whose onset date and end date are both missing.
- An AE where the onset date is missing and the end date is after the first dose date of study drug
- An AE where the onset date is missing, the end date is on the first dose date of study drug, and the end time (hh:mm) is absent or after the initiation of the first dose of study drug.

An overall summary of TEAEs will be presented to include the number and percentage of subjects with at least 1 TEAE in the following categories:

- Any TEAE
- Serious TEAE
- TEAE of CTCAE grade ≥ 3
- TEAE of maximum CTCAE Grade 3
- TEAE of maximum CTCAE Grade 4
- TEAE of maximum CTCAE Grade 5
- Infusion-related reaction
- TEAE related to any study drug
- TEAE related to TJ004309
- TEAE related to atezolizumab
- Serious TEAE related to any study drug
- Serious TEAE related to TJ004309

- Serious TEAE related to atezolizumab
- TEAE of CTCAE grade ≥ 3 related to any study drug
- TEAE of CTCAE grade ≥ 3 related to TJ004309
- TEAE of CTCAE grade ≥ 3 related to atezolizumab
- TEAE leading to any study drug discontinuation
- TEAE leading to TJ004309 discontinuation
- TEAE leading to atezolizumab discontinuation
- TEAE leading to death

In addition, the number and percentage of subjects with at least one TEAE in the following categories will be summarized by SOC and PT (unless noted otherwise below) for each cohort and overall:

- Any TEAE (summarized by SOC, PT and maximum CTCAE grade)
- Serious TEAE
- TEAE of CTCAE grade ≥ 3 (summarized by SOC, PT and maximum CTCAE grade)
- TEAE of CTCAE grade ≥ 3 related to any study drug (summarized by SOC, PT and maximum CTCAE grade)

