- TEAE of CTCAE grade ≥ 3 related to TJ004309 (summarized by SOC, PT and maximum CTCAE grade)
- Infusion-related reactions
- TEAE related to any study drug
- TEAE related to TJ004309
- TEAE related to atezolizumab
- Serious TEAE related to any study drug
- Serious TEAE related to TJ004309
- Serious TEAE related to atezolizumab
- TEAE leading to any study drug discontinuation
- TEAE leading to TJ004309 discontinuation
- TEAE leading to atezolizumab discontinuation
- TEAE leading to death

SOC/PT categories in the TEAE summaries will be sorted in a frequency decreasing order for overall. A subject who had multiple TEAEs in a SOC/PT category will only be counted

once for that category. The causal relationship between the treatment and an AE will be assessed by the Investigator. For summary purposes, if relationship to the treatment is missing for a TEAE, it will be assumed to be related to the treatment; if the CTCAE grade is missing for a TEAE, it will be assumed to be grade 3; if a subject experienced multiple TEAEs in the same SOC/PT category, the maximum CTCAE grade and the strongest causal relationship to treatment among these TEAEs will be used.

All AEs collected on the CRF page 'Adverse Events' will be listed by subject.

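### Protocol 8.3.1 and 8.3.2.2 conflict on recording disease progression, and fatal progression, an SAE whatever its cause, can enter the all-causality TEAE rows of SAP 9.1 with only partial separation.

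*Protocol*

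**What the plan says.** **Recording rules (Protocol).** Section 8.3.1 contains two lists. The list of what can be an AE includes "Worsening of signs and symptoms of the malignancy under study drug treatment". The list of what is not an AE includes "The disease/disorder being studied or its progression, signs, or symptoms, unless more severe than expected for the participant's condition". Section 8.3.2.2 then states: "Progression of the malignancy under study (including signs and symptoms of progression) should not be recorded as an AE or SAE". Its next sentence makes two exceptions. Progression is reported as an SAE if the investigator believes it is related to study drug, or if "the progression of the malignancy led to death, the progression should be reported as an SAE". The second exception does not depend on causality. The summary of changes (Section 11) describes it as a deliberate clarification. Table 10 defines Grade 5 by "Results in patient's death".

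**Analysis (SAP 9.1).** A TEAE is an AE with onset or worsening from the first dose and "up to 30 days after the last dose of study drug, or one day prior to the subsequent anti-tumor therapy, whichever occurs earlier". The definition does not mention progression. The overall summary includes rows for serious TEAEs, TEAEs of Grade 3 or higher, "TEAE of maximum CTCAE Grade 5" and "TEAE leading to death", all regardless of cause. Serious and Grade 3 or higher TEAEs also have related-only rows. The Grade 5 and fatal rows do not. SAP 9.2 lists deaths with their primary cause and plans no table of them.

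**The concern.** Two things are at stake.

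First, recording may be inconsistent. For non-fatal worsening that is not thought drug-related, a site could record it under the first list in 8.3.1, apply a severity judgement under the second list, or omit it under 8.3.2.2. Each choice agrees with some sentence of the protocol, and the choice affects the serious and Grade 3 or higher counts.

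Second, a death from cancer can be counted beside a death from toxicity in the same summary row. Safety and tolerability is the first listed secondary endpoint. SAP Section 8 says that DOR, PFS and OS will not be reported, and SAP 8.3 counts only deaths before the first response assessment. The Grade 5 and fatal TEAE rows are then the main tabulated counts of deaths in the abbreviated CSR, with no survival estimate and no table of causes beside them.

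**Working it through.** The documents state no figure on this point, so there is none to reproduce. The check is a comparison of texts, followed by an illustration of size.

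**1. The recording rules side by side**

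| Situation | 8.3.1, AE list | 8.3.1, non-AE list | 8.3.2.2 |
|---|---|---|---|
| Non-fatal worsening, as expected, not thought drug-related | AE | Not an AE | Not recorded |
| Non-fatal worsening, more severe than expected, not thought drug-related | AE | Can be an AE | Not recorded |
| Progression believed drug-related | AE | Depends on severity | SAE |
| Progression leading to death | AE | Depends on severity | SAE, whatever the causality |

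The conflict lies between the two lists in 8.3.1, and between 8.3.1 and 8.3.2.2. In the second row, 8.3.2.2 has no counterpart to the more-severe-than-expected qualifier.

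**2. From a fatal progression to the tables**

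- Under 8.3.2.2 it is an SAE, so it is serious.
- Under Table 10 an event that results in death is Grade 5, so it is also Grade 3 or higher.
- Protocol 8.4 requires AEs to be entered on the Adverse Event eCRF. That implies, without spelling out, that this SAE is entered there too.
- If the recorded onset falls in the SAP 9.1 window, it is a TEAE. The documents do not say whether onset means the date of progression or the date of death.
- It then counts in four all-causality rows of the overall summary: serious, Grade 3 or higher, Grade 5 and fatal.

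**3. What separates it again**

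- The serious and fatal tables by SOC and PT, and the Grade 3 or higher table by SOC, PT and maximum grade, give a progression term its own line if it is coded as progression.
- The related Grade 3 or higher tables by maximum grade show related Grade 5 events.
- There are related-only serious tables, and the SAP 9.2 listing gives the primary cause of each death.
- The overall summary has no related row for Grade 5 or fatal TEAEs, and no cause-of-death table is planned.

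**4. Illustration of size**

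N = 60 is the planned maximum (up to 30 in each of two cohorts). Every event count below is an assumption. The rate is x/N. The exact 95% Clopper-Pearson limits are the 0.025 quantile of Beta(x, N−x+1) and the 0.975 quantile of Beta(x+1, N−x). For x = 0 the lower limit is 0.

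| Assumed progression deaths counted as TEAEs | Fatal row with 0 toxic deaths | Fatal row with 1 toxic death |
|---|---|---|
| 0 | 0/60 = 0% (0 to 6.0) | 1/60 = 1.7% (0.0 to 8.9) |
| 1 | 1/60 = 1.7% (0.0 to 8.9) | 2/60 = 3.3% (0.4 to 11.5) |
| 3 | 3/60 = 5.0% (1.0 to 13.9) | 4/60 = 6.7% (1.8 to 16.2) |
| 6 | 6/60 = 10.0% (3.8 to 20.5) | 7/60 = 11.7% (4.8 to 22.6) |

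The chance that at least one such event occurs is 1 − (1 − q)^N, where q is the assumed risk per subject:

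| q | N = 30 | N = 60 |
|---|---|---|
| 2% | 45% | 70% |
| 5% | 79% | 95% |
| 10% | 96% | 99.8% |

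**The case against.** The case on the other side is substantial, and several stronger readings fail against it.

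- **That 8.3.2.2 contradicts itself.** It does not. The sentence on fatal progression is a stated exception to the sentence before it.
- **That progression is counted only when it kills.** It is not. Section 8.3.2.2 also excepts progression believed drug-related, and 8.3.1 leaves a route for progression more severe than expected.
- **That the tables are certain to mix cancer deaths with toxicity.** This is not established. It needs a fatal progression with onset inside the window, the onset convention is unstated, and the window closes early if another anti-tumor therapy starts. Eligibility requires ECOG 0 or 1 and a life expectancy of at least 12 weeks.
- **That the fatal row would be read as drug toxicity.** An AE need not be causal under 8.3.1, and the rows stand beside others labelled as related. SAP 9.1 treats missing causality as related, but Protocol 8.4.3 requires a causality assessment before an SAE is first sent, so that rule should seldom reach a fatal event.
- **That the SAP offers no separation.** The SOC/PT tables, related-only tables and death listing let a careful reader recover much of it.

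It is also fair to say that the trial is single-arm with descriptive safety tables, that 60 is a ceiling, and that rewriting the recording rule cannot change events already recorded. SAP 4.1 already describes Part 2 as not initiated. What survives is the conflict in the recording rules, and overall-summary rows that cannot be split by cause without going to other outputs.

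**Conclusion.** The point holds in limited form. Protocol 8.3.1 and 8.3.2.2 do not give one rule for recording progression, so non-fatal worsening may be handled differently by site. Whether sites did differ cannot be shown from the documents. Fatal progression is deliberately brought in as an SAE whatever its causality, and nothing in the SAP 9.1 TEAE definition keeps it out of the all-causality rows when onset falls in the window. Other planned outputs separate it in part. The overall summary does not, and it lacks a related-fatal row.

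The size is unknown. The documents give no rate of death from progression, so the illustrated counts, including zero, are assumptions, and the intervals only restate them. Under an assumed risk of 2% per subject or more, at least one such event among 60 is more likely than not, but not certain. This is worth correcting before the tables are produced. It does not affect the primary endpoint.

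**What to change.** 1. **Protocol 8.3.1 and 8.3.2.2:** reconcile them into one recording rule for progression and its signs and symptoms. If data are already collected, state in the CSR how progression was recorded, including which date was used as onset for fatal events.
2. **SAP 9.1, overall summary:** present serious, Grade 3 or higher, Grade 5 and fatal TEAEs twice, once for all events and once without progression of the malignancy under study. Identify progression by preferred term and, for deaths, also by the recorded primary cause.
3. **SAP 9.1, overall summary:** add a row for related TEAEs leading to death.
4. **SAP 9.2:** tabulate deaths by primary cause as well as listing them.

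The cost is a few extra rows, one small table and a reconciled paragraph or CSR statement. No new data are needed. The main weakness is that preferred terms alone may miss progression coded to an organ-specific term. For deaths the recorded primary cause offers a cross-check, but for non-fatal events the gap remains and should be stated in a footnote.

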## 8.4 Safety Reporting Requirement

The Investigator is responsible for ensuring that all AEs are detected, documented, and recorded on the Adverse Event eCRF.

Each study patient will be questioned about AEs at each clinic visit following initiation of treatment. Open-ended and non-leading verbal questioning of the patient/patient's legal guardian is the preferred method to inquire about AE information. Examples of non-directive questions include the following:

"How have you felt since your last clinic visit?"

"Have you had any new or changed health problems since you were last here?"

For each AE recorded on the Adverse Event eCRF, the Investigator will make an assessment for seriousness, severity and causality (see [Section 8.4.2](#)).

